7.3 Reported Adverse Events (clinicaltrials.gov template sections)

AE Reporting Timeframe: Safety data will be collected from the time of informed consent until 28 days from Day 1. Patients who are hospitalised will be followed for up to 28 days after they are discharged.

All-Cause Mortality will be presented as per the clinicaltrials.gov template as follows:

Total	All Cause Mortality	Treatment arm		Control arm	
		Affect/At Risk (%)	# Events	Affect/At Risk (%)	# Events

Serious Adverse events will be presented as per the clinicaltrials.gov template as follows:

Total	<AE term>	Treatment arm		Control arm	
		Affect/At Risk (%)	# Events	Affect/At Risk (%)	# Events

Other (non-Serious) Adverse events will be presented as per the clinicaltrials.gov template as follows:

Frequency Threshold Above Which Other Adverse Events are Reported: 0%<TBC>

Total	<AE term>	Treatment arm		Control arm	
		Affect/At Risk (%)	# Events	Affect/At Risk (%)	# Events

7.4 Endpoints/outcome measures to be reported

Primary and secondary endpoints will be reported on the clinicaltrials.gov website as outcome measures as follows. All secondary endpoint data will be taken from Table 9 and PK data relating to the PK secondary endpoint will be taken from the PK final report.

Primary Objective and Endpoint		Endpoint	Outcome Measures
To further assess the safety and toxicity profile of camostat, to support integration into a Phase III trial.	Causality and severity of each adverse event (AE) to camostat.		
Measure Title: Number of camostat related AEs and SAEs.
 
Measure Description: Number of camostat related AEs and SAEs
 
Measure Title: Number of AEs by severity grade
 
Measure Description: Number of AEs by severity grade (mild, moderate, severe)
 
Information to be presented: Refer to programmed table "Primary endpoint reporting for clinicaltrials.gov"

			Time frame: Days 1-28
Secondary Objectives and Endpoints		Endpoint	
To confirm that the PK profile aligns with the established PK profile for the active metabolite of camostat, 4-(4-Guanidinobenzoyloxy)phenylacetic acid (GBPA).	Confirm PK parameters of GBPA as assessed by population estimates from population PK analysis (popPK).		
Measure Title: PK parameter Maximum concentration (Cmax) of 4-(4-Guanidinobenzoyloxy)phenylacetic acid (GBPA).
 
Measure Description: Maximum concentration (Cmax) of GBPA as assessed by population estimates from population PK analysis
 
Time frame: Days 7 and 14

Information to be presented: Mean and standard deviation for each arm at each time point for each arm (to be provided in final PK report).
	
Measure Title: PK parameter area under the curve (AUC) of GBPA

Measure Description: Area under the curve (AUC) of GBPA, as assessed by population estimates from population PK analysis
	
Time frame: Days 7 and 14
 
Information to be presented: Mean and standard deviation for each arm at each time point for each arm (to be provided in final PK report).

Measure Title: PK parameter time to maximum concentration (Tmax) of GBPA, as assessed by population estimates from population PK analysis
	
Measure Description: Time to maximum concentration (Tmax) of GBPA, as assessed by population estimates from population PK analysis

	
Time frame: Days 7 and 14
 
Information to be presented: Median and range for each arm at each time point for each arm (to be provided in final PK report).

	
Measure Title: PK parameter to confirm half-life (T1/2) of GBPA

	
Measure Description: Half-life (T1/2) of GBPA as assessed by population estimates from population PK analysis

		
Time frame: Days 7 and 14
 
Information to be presented: Mean and standard deviation for each arm at each time point for each arm (to be provided in final PK report).

To assess the ability of camostat to reduce the requirement for COVID-19 related hospital admission in community patients with SARS-CoV-2 infection.	
Rate of COVID-19 related hospital admission in community patients with SARS-CoV-2 infection.
	
Measure Title: Number of community patients admitted to hospital due to COVID-19
 
Measure Description: Number of community patients admitted to hospital due to COVID-19
 
Time frame: Days 1-28
 
Population description: Patients who received camostat for a minimum of five days (treatment arm) or who either completed up to Day 14 or came off trial at an earlier timepoint due to an endpoint defined reason (e.g. hospitalisation).
 
Information to be presented: Number of community patients admitted to hospital due to COVID-19 in each arm from programmed table.

To evaluate the requirement for supplementary oxygen (non-invasive or mechanical invasive) in patients who have received camostat as treatment for SARS-CoV-2 infection.	
Supplementary oxygen-free days at 28 days (from randomisation).
	
Measure Title: Number of oxygen free days
 
Measure Description: Number of oxygen free days
 
Time frame: Days 1-28
 
Population description: Patients who received camostat for a minimum of five days (treatment arm) or who either completed up to Day 14 or came off trial at an earlier timepoint due to an endpoint defined reason (e.g. hospitalisation).

		Information to be presented: Median and range of oxygen free days by treatment arm (provided in Stats report).
To evaluate the requirement for ventilation in patients who have received camostat as treatment for SARS-CoV-2 infection.	Ventilator-free days at 28 days (from randomisation).	
Measure Title: Number of ventilator - free days
 
Measure Description: Number of ventilator - free days
 
Time frame: Days 1-28
 
Population description: Patients who received camostat for a minimum of five days (treatment arm) or who either completed up to Day 14 or came off trial at an earlier timepoint due to an endpoint defined reason (e.g. hospitalisation).

		
Information to be presented: Median and range of ventilator free days by treatment arm (provided in Stats report).
 
Measure Title: Time to worst point on the scale or deterioration of two points or more (from randomisation) on 9 point category ordinal scale.
 
Measure Description: Median time and range to worst point on the scale or deterioration of two points or more (from randomisation) on 9 point category ordinal scale
 
Time frame: Days 1-28
 
Population description: Patients who received camostat for a minimum of five days (treatment arm) or who either completed up to Day 14 or came off trial at an earlier timepoint due to an endpoint defined reason (e.g. hospitalisation).

	
5. Hospitalised – severe disease, non-invasive ventilation or high-flow oxygen
 
6. Hospitalised – severe disease, intubation and mechanical ventilation
 
7. Hospitalised – severe disease, ventilation and additional organ support – vasopressors, renal replacement therapy (RRT), extracorporeal membrane oxygenation (ECMO)
 
8. Death
	Information to be presented: Median and range of times to worst point on the ordinal scale (provided in Stats report).
--	--	--

8 TABLES LISTINGS AND FIGURES

8.1 LISTINGS:

Completed or Discontinued patients

Treatment compliance End of monitoring period (Control arm)

End of study

Protocol deviations

Patients excluded from efficacy analysis

Screening failures

EnrolmentDemographic and Baseline Data

Demographics

Randomisation

Medical history

Risk factors

COVID-19 symptoms

Influenza or COVID-19 Vaccination

Concomitant medications

Medical procedures

Compliance and/or Drug Concentration Data

Treatment compliance Efficacy Response Data

9-point ordinal scale for clinical improvement

COVID-19/Camostat related hospitalisation details

Oxygen therapy and ventilation

Hospitalisation follow up

Safety Data

Adverse Events (by subject)

Adverse Events by SOC

Pregnancy test

Laboratory results

Imaging

8.2 TABLES

Demographic Data

Baseline characteristics by treatment arm

Reasons for patient withdrawal / completion

Compliance

Treatment modifications and/or non-compliance (treatment arm only)

Efficacy Data

Ordinal Scale

Summary of Secondary Endpoint Data

Safety Data

Overview of Treatment Emergent Adverse Events (Inclusive and post Day 1)

Frequency of All Adverse Events

Frequency of pre-treatment AEs

Frequency of TEAEs

Frequency of All Camostat related treatment emergent AEs

Frequency of all COVID-19 related treatment emergent AEs

Frequency of all treatment emergent SAEs

Breakdown of TEAEs leading to Patient withdrawal

Neutrophils:Lymphocytes ratio per patient (treatment and control arm respectively)

APPENDIX – STATISTICAL ANALYSIS PLAN

SPIKE-1 TRIAL: A Randomised Phase II trial in early COVID-19, assessing use of camostat by blocking SARS-CoV-2 Spike protein-initiated membrane fusion.

Statistical Analysis Plan

CONFIDENTIAL

Version No	Final 1.0	
Date Finalised	27 Sep 2021	
Author(s)		1
CI Email address		
Funder Name	LifeArc	
Sponsor Name	Cancer Research UK	
EudraCT Number	2020-002110-41	

Document Control		
Version No	Date	Summary of Revisions
1.0	27Sep2021	Initial Creation
2.0	16Feb2022	Edits following changes to RAP

Contents

List of Abbreviations	34
1. Introduction	35
2. Statistical Methods section from the protocol	35
3. Overall Statistical Principles	36
3.1 Populations	36
3.2 Missing data.....	36
3.3 Adjusting for centre	36
3.4 Subgroup analyses.....	37
4. List of Analyses.....	37
4.1 Interim evaluation.....	37
4.2 Main study findings	37
4.1 Transformations.....	38
4.2 Tables	Error! Bookmark not defined.
5. Validation and QC	38

LIST OF ABBREVIATIONS

Abbreviation	Full name
AE	Adverse Event
CI	Confidence interval
IQR	interquartile range
ITT	Intention-to-treat
NLR	Neutrophil to lymphocyte ratio
PK	Pharmacokinetics
RT-PCR	Reverse transcription polymerase chain reaction
QC	Quality control
qPCR	Quantitative polymerase chain reaction

INTRODUCTION

This Statistical Analysis Plan is based on protocol version 6.0, dated 20 Sep 2021.

This is a Phase II randomised, multicentre, prospective, open label, clinical trial of camostat (200mg four times per day) vs best supportive care for adult patients (≥ 18 years) with validated COVID-19. Patients will be recruited from testing centres which may include primary care 'COVID-19 hub' clinics, COVID-19 community-based testing centres or equivalent clinical environments. Patients may be recruited in hospital if hospitalised for reasons other than COVID-19 and who have tested positive while in hospital. Patients will be randomised 1:1 into each arm. Patients will be stratified into four groups: Males 65 years or older; males below 65 years, females 65 years or older; females below 65 years. Up to 100 patients will be recruited, in a 1:1 ratio between treatment and control.

See section 13.2 of the protocol for the sample size calculation.

10 STATISTICAL METHODS SECTION FROM THE PROTOCOL

The primary outcome will be an exploration of camostat safety and toxicity, in terms of the number and severity of AEs and SAEs. Recruitment rate will be reported as numerator and denominator, with the percentage and exact binomial 95% confidence interval. The other feasibility measures will be reported in the same way.

Descriptive statistics will be used to describe the demographics for each randomised group and overall. For categorical data, frequencies will be reported, and for continuous variables means and standard deviations, or for skewed data, medians and interquartile ranges will be reported.

Secondary outcomes will be reported in a similar way to the demographic data, with an estimate of the difference and standard error between the treatment groups for continuous or ordinal scale data. Medians and IQRs will be used where data are non-normally distributed. Absolute percentage difference and standard error will be reported for binary variables. Kaplan-Meier plots and life tables will be used to estimate median survival times.

Subgroups will be explored where there are sufficient patients in each group. Data will be split by age (< 65 years vs ≥ 65 years), fall in lymphocyte (<20% fall vs $\geq 20\%$ fall), and neutrophil:lymphocyte ratio (<2.18 vs ≥ 2.18) for key explanatory variables.

No significance testing will be performed. Differences between treatment groups will be reported solely to inform future trials.

All enrolled patients who receive at least one dose of camostat in the treatment arm and complete Day 1 in the control arm will be evaluable for safety.

In order to be evaluable for efficacy, treatment arm patients must receive camostat for a minimum of five days, and control arm patients must either complete up to Day 14 or come off trial at an earlier timepoint due to an endpoint (e.g. hospitalisation).

Safety data will be collected from the date of written or verbal consent. Safety variables will be summarised by descriptive statistics.

Adverse events will be reported as tables of frequency of AEs by MedDRA system organ class and by worst severity grade observed. Tables should indicate related and unrelated events

Adverse events will be reported for each arm and presented as tables of frequency of AEs by MedDRA system organ class and by worst severity grade observed. Tables will indicate related and unrelated events

11 OVERALL STATISTICAL PRINCIPLES

Analysis of the data will primarily be performed using the SAS statistical package (SAS software. Copyright © 2002-2012 SAS Institute Inc. SAS and all other SAS Institute Inc. product or service names are registered trademarks or trademarks of SAS Institute Inc., Cary, NC, USA.). The statistical significance level will be $p=0.05$, although as a feasibility study, few hypothesis tests will be conducted.

11.1 Populations

The efficacy population will only include patients from the camostat arm where they have completed 5 days of treatment and in the control arm where they have completed 14 days of treatment or reached an endpoint (eg hospitalisation). All primary and secondary analyses will be conducted with this population. An intention-to-treat analysis of the main secondary outcomes (COVID-19 related hospital admissions, supplementary oxygen-free days, ventilator-free days, time to worst point on the 9-point ordinal scale) will also be conducted, should the data allow.

Patients who agree to the taking of blood samples will be included in the analysis of the PK data. The mean and SD will be reported at each time point (Days 7 and 14), as will the mean changes. The data may be log (or other) transformed if not normally distributed. [REDACTED]

[REDACTED] Change will be
change from previous blood test.

The safety population will include all patients with at least one dose of treatment (camostat or control). Safety data will be collected from the date of written consent. Safety variables will be summarised by descriptive statistics.

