5.1 Patient Populations

The analysis sets are defined as follows:

Full Analysis Population (FAP):	All enrolled patients.
	Patients who are enrolled in error onto the trial (due to ineligibility/administrative error), prior to receiving study treatment, will be excluded from the FAP.
Safety Population:	All enrolled patients who received at least one dose of camostat (or complete Day 1 of the control arm). Safety data will be collected from the date of written consent.
Efficacy Population:	Treatment arm patients must receive camostat for a minimum of five days, and control arm patients must either complete up to Day 14 or come off trial at an earlier timepoint due to an endpoint (e.g. hospitalisation).
Pharmacokinetic Population:	All enrolled patients who received one dose of camostat (or complete Day 1 of the control arm) – PK sample required (optional).

All other populations will be the same definition as Efficacy Population as defined above.

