6.6 Safety

Descriptive statistics will be used for evaluation of safety. The incidence of AEs will be summarised and displayed in frequency tables using counts and percentages. Additional parameters including but not limited to [REDACTED], and laboratory results will also be considered when evaluating safety.

Deaths, serious adverse events (SAEs) and events resulting in trial discontinuation will be tabulated.

Additional safety analyses may be determined at any time, in order to most clearly enumerate rates of toxicities and to further define the safety profile of camostat.

- The safety population is composed by all patients that receive at least one dose of camostat / complete Day 1 of control arm. The safety patient population will be used for the general safety presentations.

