12 LIST OF ANALYSES

Although the sample size has been calculated on recruitment rate, the primary outcome will be the comparison of adverse events and their severity between treatment arms. These will be listed overall and by strata.

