12.2 Main study findings

The primary outcomes for this trial are safety and adverse events. These will be tabulated by treatment group and by strata/subgroups. Pregnancy, compliance, protocol deviations will also be tabulated in this way.

The majority of secondary outcomes will be reported in the main RAP. The secondary outcomes of number of oxygen-free days, ventilator-free days, and number of days to worst point on the 9-point ordinal scale (see secondary objectives in RAP for definitions) will be reported as median and range for the 28 days of follow up post-randomisation.

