12.3 Transformations

12.4 Outputs

Tabular outputs have been described in the main RAP. The following analyses will be in addition to these tables.

Population: Efficacy population (at least 5 days of camostat/14 days of control)

Medians and range for the following variables will be produced by treatment group:

- Number of oxygen-free days,
- Number of ventilator-free days,
- Number of days to worst point on the 9-point ordinal scale

Kaplan-Meier plots of the following variables will be produced by treatment group:

- Time to worst point on ordinal scale

Plots of daily data will also be produced where this will aid interpretation.

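### SAP 11.1 puts the primary adverse-event analysis on the efficacy population, against the safety population used elsewhere; the by-strata and registry safety outputs name no population

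*SAP*

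**What the plan says.** The SAP document has two parts: a reporting plan (sections 2 to 9, called the RAP) and an appended statistical analysis plan (from section 10).

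- **Primary outcome.** Protocol 13.1 and SAP 10 make it the number and severity of AEs and SAEs. SAP 12 says "the primary outcome will be the comparison of adverse events and their severity between treatment arms".
- **Population for the primary analysis.** SAP 11.1 first defines the efficacy population, then says: "All primary and secondary analyses will be conducted with this population". No other population has been named by that point in the section.
- **Population for safety.** SAP 5.1 defines it as "All enrolled patients who received at least one dose of camostat (or complete Day 1 of the control arm"). SAP 6.6 says: "The safety patient population will be used for the general safety presentations". Tables 5, 6 and 7 in SAP 6.7 are headed as safety-population tables. Protocol 13.1 and SAP 10 use the same rule of one dose or control Day 1.
- **A second safety definition.** The last paragraph of SAP 11.1 reads: "The safety population will include all patients with at least one dose of treatment (camostat or control"). It does not say which analyses use that set.
- **Outputs with no population named.** SAP 12 lists AEs overall and by strata. SAP 12.2 says of the primary outcomes: "These will be tabulated by treatment group and by strata/subgroups". The registry primary measure in SAP 7.4 includes "Number of AEs by severity grade (mild, moderate, severe"), with no population description, although the clinical secondary measures in the same section each carry one.
- **Where the efficacy label is explicit.** SAP 12.4 has "Population: Efficacy population (at least 5 days of camostat/14 days of control"), covering oxygen-free days, ventilator-free days and time to worst point on the ordinal scale.

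**The concern.** The primary objective is to characterise safety in support of a Phase III trial. A safety analysis restricted to patients who tolerated at least five days of drug excludes the people most likely to show early intolerance. The treatment-arm rule has no exception for patients who stop early because of an AE or an endpoint. The control-arm rule does keep patients who leave early because of an endpoint, so the exclusion is not the same in the two arms.

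Two programmers following different sections would produce different primary results. The stratified, severity and registry summaries could then disagree with Tables 5 to 7 and could look safer. No significance test depends on this, but the reported primary result does.

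**Working it through.** **1. The plan's own figure.** No figure in the plan bears directly on this point. The only precision statement is in protocol 13.2: a recruitment rate of 50%, standard error 3.5%, 95% CI 43% to 57%. With 100 recruited at 50%, 200 are approached: √(0.5 × 0.5 / 200) = 3.54%, and 50% ± 1.96 × 3.54% = 43.1% to 56.9%. It reproduces and does not depend on the choice of population.

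**2. Which population each primary-outcome output gets.**

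| Output | Where | Population stated |
|---|---|---|
| All primary analyses | SAP 11.1 | Efficacy |
| General safety presentations | SAP 6.6 | Safety |
| AE Tables 5 to 7 | SAP 6.7 | Safety |
| AEs overall and by strata | SAP 12 | None |
| AEs by arm and strata/subgroup | SAP 12.2 | None |
| Registry AE tables | SAP 7.3 | None |
| Registry primary measure | SAP 7.4 | None |

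The primary outcome is safety, and there is no primary efficacy outcome to which the word primary in 11.1 could refer. The first row therefore contradicts the second and third. The last four rows are left to a choice between 11.1 and 6.6. The programmed table that feeds the registry primary measure is not in the table list in SAP 8.2, so its population cannot be found there either.

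**3. Severity.** Protocol 13.1 and SAP 10 call for AE tables by worst severity grade. Neither the shells of Tables 5 to 7 nor the list in SAP 8.2 shows grade. Severity by arm therefore rests on general statements and the unlabelled registry entry.

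**4. How early events leave the set.** Protocol 5.3.3 ties a possible, probable or highly probable causal assessment to treatment withdrawal, with restart possible after at most 48 hours of interruption. Protocol 12.3 leaves removal from treatment to the investigator and lets patients stop for an intolerable AE. These two sections should be reconciled. Under either, a patient can stop before five days because of an AE.

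**5. Possible size (assumed counts).** Take 50 camostat patients (the planned maximum per arm), L patients with later AEs, and k patients whose AE led them to stop before five days. The safety-set rate is (L + k)/50; the efficacy-set rate is L/(50 − k).

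| L | k | Safety set | Efficacy set | Gap (points) |
|---|---|---|---|---|
| 5 | 1 | 6/50 = 12.0% | 5/49 = 10.2% | 1.8 |
| 5 | 3 | 8/50 = 16.0% | 5/47 = 10.6% | 5.4 |
| 5 | 5 | 10/50 = 20.0% | 5/45 = 11.1% | 8.9 |
| 20 | 1 | 21/50 = 42.0% | 20/49 = 40.8% | 1.2 |
| 20 | 3 | 23/50 = 46.0% | 20/47 = 42.6% | 3.4 |
| 20 | 5 | 25/50 = 50.0% | 20/45 = 44.4% | 5.6 |

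**6. By stratum.** Four age-by-sex strata evenly filled give 50/4 = 12.5 camostat patients each. With one early stopper with an AE and one later AE patient:

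- 12 patients: 2/12 = 16.7% against 1/11 = 9.1%.
- 5 patients: 2/5 = 40.0% against 1/4 = 25.0%, a gap of 15.0 points.
- 20 patients: 2/20 = 10.0% against 1/19 = 5.3%, a gap of 4.7 points.

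**7. Direction.** The safety-set rate is a weighted average of the rates in retained and excluded patients. The efficacy set therefore understates the rate exactly when AEs are more common among the excluded than overall. If early stoppers mostly have no AE, it overstates: with L = 20, one early stopper with an AE and four without, 21/50 = 42.0% against 20/45 = 44.4%.

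**8. The control-arm definition.** Controls receive best supportive care and take no study dose, so a one-dose rule cannot be applied to them. Protocol 13.1 and SAP 5.1 give a workable rule: Day 1 completed. The opening text of SAP 5 gives no control rule at all.

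**The case against.** The best reply is that the intent is clear. SAP 11.1 itself defines a safety population, which would be pointless if AEs were analysed elsewhere. SAP 6.6 and Tables 5 to 7 use that set, and SAP 12.4 defers tabular outputs to the reporting plan. On this view the defect is one misplaced word and some missing labels. A blank in the registry plan also proves little: the PK measures have no population description either, and the efficacy definition is written out for each clinical secondary measure. The missing severity grade is a table-shell gap rather than a population conflict in itself.

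The size is also open to challenge. The counts are invented, the control-arm exclusions are not quantified, and step 7 shows that the direction can reverse. The registry measures are numbers of AEs, so patient percentages do not describe them.

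Most of this stands as a limit on the consequence. The overall AE tables are safe, early stoppers would still appear in Table 7, and the bias is possible rather than demonstrated. It does not remove the conflict. Evidence of intent does not delete the word primary from 11.1. The by-strata AE tables are absent from the list in SAP 8.2, so deferring to that list gives them no label. A bias that could run either way is no argument for the efficacy set as the basis of a safety analysis.

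**Conclusion.** The concern holds. SAP 11.1 states a rule that is wrong for the primary outcome and contradicts the protocol and the rest of the SAP. This is more than missing detail, and it should be fixed before analysis. Confidence in the textual conflict is high.

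The numerical effect cannot be derived from the documents. Under the assumed counts in the working, the camostat-arm AE rate falls by 1.2 to 8.9 points overall. With one early stopper and one later AE patient, it falls by 4.7 to 15.0 points in strata of 20 down to 5 patients. These figures assume that every excluded camostat patient had an AE. With no such patients, the two sets differ only through other exclusions. The effect on the between-arm comparison is unknown, because control exclusions are not quantified.

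**What to change.** 1. In SAP 11.1, limit the sentence to the secondary efficacy analyses.
2. State that all primary AE and SAE analyses use the safety population. Name it on each output: the by-strata and subgroup results in SAP 12 and 12.2, a severity-by-arm summary, and the registry entries in SAP 7.3 and 7.4.
3. Replace the safety definition in SAP 11.1 with the rule in protocol 13.1: at least one camostat dose, or Day 1 completed in the control arm. Add the control rule to the opening text of SAP 5.
4. If an AE summary in patients with at least five days of dosing is wanted, label it supplementary. None is separately planned now.

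The cost is a few lines of text and some output labels. It needs no new data and no change to the sample size.
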